Cover page for clinicaltrials.gov

Study Title	Determining the Implicit and Rule-based Learning Ability of Individuals With Aphasia to Better Align Learning Ability and Intervention
NCT Number	05119023
Document Description	IRB approved protocol
Document Date	Document version date = 8/30/22

PARTNERS HUMAN RESEARCH COMMITTEE PROTOCOL SUMMARY

Answer all questions accurately and completely in order to provide the PHRC with the relevant information to assess the risk-benefit ratio for the study. Do not leave sections blank.

PRINCIPAL/OVERALL INVESTIGATOR

[name]

PROTOCOL TITLE

Determining the implicit and rule-based learning ability of individuals with aphasia to better align learning ability and intervention

FUNDING

NIH NIDCD R21 DC019203-01

VERSION DATE

Version 7: 8/30/22

SPECIFIC AIMS

Concisely state the objectives of the study and the hypothesis being tested.

The objective of this study is to examine learning in individuals with post-stroke aphasia (acquired language impairment). We aim to determine a behavioral phenotype of learning for people with aphasia (PWA), examining how cognitive-linguistic variables and stroke characteristics (lesion size and location) relate to learning.

To this end, the aims are as follows:

Aim 1. Determine the presence of selective deficits in observational (implicit) and rulebased learning in individuals with aphasia. Participants in our study will be stratified in to one of four learning profiles: learning under (a) both conditions, (b) rule-based conditions only, (c) observational conditions only, and (d) no condition. Pilot work conducted in eighteen individuals with aphasia has identified equal percentages of learners of type a, c and d (20% of pilot participants in each stratification) with 40% showing learning under rule-based conditions only, supporting the hypothesis that differences in learning profile arise among PWA.

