During aphasia rehabilitation, patients are guided to relearn language, reaccess language or regain functional use of language via therapies that involve stimuli, tasks, cues and feedback (see Horton, 2006). Consequently, the process of therapy implicitly engages many mechanisms of learning that need to be systematically considered in aphasia. Evidence is emerging to suggest that nonlinguistic learning is impaired in individuals with aphasia (Schuchard & Thompson, 2014; [name] & Kiran, 2013a; [name] & Kiran, 2013b); and furthermore, that PWA develop strategies less consistently and less effectively than non brain-damaged controls ([name] & Kiran, 2015). We suggest that the contribution of underlying cognitive systems is essential to relearning in aphasia and that understanding the behaviors associated with learning are critical for our understanding of the mechanisms of therapy and ways to better tailor treatment to individuals.

In aphasia, little is understood about how task and treatment manipulations impact patient behaviors and progress with therapy. We propose to thoroughly examine the behaviors of learning and the cognitive-linguistic and lesion characteristics that relate to learning, to characterize a phenotype of learning for individuals with aphasia, setting the foundations for intervention studies aimed at individually tailoring treatment and improving the predictability of outcomes.

RESEARCH DESIGN AND METHODS

Briefly describe study design and anticipated enrollment, i.e., number of subjects to be enrolled by researchers study-wide and by Partners researchers. Provide a brief summary of the eligibility criteria (for example, age range, gender, medical condition). Include any local site restrictions, for example, "Enrollment at Partners will be limited to adults although the sponsor's protocol is open to both children and adults."

Study Design

In this cross-sectional study, 75 participants will complete language and cognitive assessments and behavioral tests of learning. A subset of participants will also complete a structural magnetic resonance imaging (MRI) scan to obtain structural brain images.

Sessions 1 & 2 described above, may take 3 sessions. If an additional session is needed, participants may complete this session in person or over Zoom based on preference. Session 3 described above, may be broken into 2 sessions based on participant scheduling preference.

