Participants will be tested over three to five sessions during which they will complete: (a) behavioral testing, (b) structural scanning. We anticipate that behavioral sessions (a) and (b) will take around 6 to 7 hours to complete.

- (a) Behavioral testing: Participants will be asked to come to research facilities at the MGH-Institute of Health Professions for behavioral testing. During these sessions, participants will complete standardized cognitive-linguistic assessments and computer-based observational and rule-based tasks, that allow for collection of accuracy, response time and eye gaze data. Most participants are expected to complete behavioral tasks in two to three, two-hour sessions. Some participants may prefer to schedule shorter, and more frequent test sessions and this will be accommodated, and tasks that can be administered over Zoom without affecting data quality (such as those that do not collect response times) can be collected over Zoom if preferred by participants.
- (b) Structural scanning:-The majority of participants will also complete a structural magnetic resonance imaging (MRI) scan in a 3Tesla scanner at the MGH Athinoula A. Martinos Biomedical Imaging Center to obtain structural images of their brain.

In order to participate in brain scans, participants must:

- be safe to participate as determined by the MR eligibility criteria outlined under eligibility, and
- produce scores of learning on at least one behavior learning task that are above chance. Since brain scan data are being utilized to evaluate and predict learning profile, individuals must show learning on at least one task.

High resolution clinical MRI scans from hospitalizations may be available for some participants. These scans will be requested, and if judged to be of high quality (e.g. no evidence of motion artifact, whole brain coverage, axial slices with voxels smaller than 3mm) participants may not need to participate in the structural scan at the MGH Athinoula A. Martinos Center for Biomedical Imaging. Scanning will occur on a separate day or on one of the behavioral testing days.

Eligibility criteria are as follows:

- Be between the ages of 18 and 80 years of age
- Have aphasia due to left hemisphere stroke per report and need for speech language therapy
- Be in the chronic stages of aphasia, at least 6 months post onset of stroke
- Report pre-morbid native-speaker level fluency in American English

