Extensive, partially-overlapping neural networks have been identified to support implicit and rule-based learning. In proposed regression models, we first propose to include percent spared tissue in those ROIs that have shown differential activation in observational versus rulebased learning. Thus, for observational learning, the striatum, which shows enhanced engagement in implicit over rule based learning will be included (e.g. Destrebecqz et al., 2005; Peigneux et al., 2000; Schendan et al., 2003) along with composite scores of visual attention, as attention has been found to be important for implicit learning (e.g. Franklin et al., 2016; Seger 1994). We will evaluate the statistical significance of a regression model with two predictors: percent spared tissue in the striatum and cognitive scores of attention, evaluating the statistical significance of the model and variability accounted for.

For rule-based learning, studies have identified the prefrontal cortex as an important neural substrate that shows increased engagement in rule-based relative to observational learning (e.g. Byrne et al., 2016; Milton et al. 2009; Panuikov & Davis, 2018; Tracey et al., 2003). Verbal working memory and executive functions also play a rule in rule management and shifting (e.g. Carpenter et al., 2016). Thus, we will evaluate the statistical significance of a regression model with three predictors: percent spared tissue in the prefrontal cortex and cognitive scores of working memory and executive function, evaluating the statistical significance of the model and variability accounted for.

Power estimations and justification of sample size. Power analysis for a multiple regression with two predictors was conducted in G*Power to determine a sufficient sample size using an alpha of 0.05. Using an effect size $f^2 = 0.25$, based on correlations of .38 between striatal activation and implicit learning (Peigneux et al., 2000) and on correlation values of .32 between attention and implicit learning from pilot data, with a sample size of 50 we will have power greater than .90 to detect significant effects.

For rule-based learning, a power analysis was conducted in G*Power including 3 predictors. An effect size f² of .28 was estimated based on correlations between prefrontal

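### Every stated Aim 2 model needs spared-tissue data, so the cognitive predictions are tested only in people with usable MRI, a sample partly selected on learning

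*Combined protocol and SAP*

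**What the plan says.** Under Specific Aims, Aim 2 makes five predictions. Two concern brain regions (striatum, prefrontal cortex) and three concern cognition (attention, verbal working memory, executive function).

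Under Research Design and Methods, Study Design, "75 participants will complete language and cognitive assessments and behavioral tests of learning". MRI is for fewer people: "A subset of participants will also complete a structural magnetic resonance imaging (MRI) scan to obtain structural brain images". The paragraph on structural scanning calls them the majority but gives no number. Besides being MRI safe, people entering the study scan must "produce scores of learning on at least one behavior learning task that are above chance". If a good-quality hospital scan exists, "participants may not need to participate in the structural scan".

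Under Brief overview of statistical methods, Aim 2, Data Analyses, three outcomes are named (SRT observational, AGL observational, rule-based) and two predictor sets are specified. For observational learning: "We will evaluate the statistical significance of a regression model with two predictors: percent spared tissue in the striatum and cognitive scores of attention". For rule-based learning: a "regression model with three predictors: percent spared tissue in the prefrontal cortex and cognitive scores of working memory and executive function". Power is stated at N=50 for the first set and N=49 for the second. The enrolment above that is attributed to attrition and to people who do not learn the tasks.

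**The concern.** Both predictor sets contain percent spared tissue. A regression cannot use a person whose predictor is missing unless the plan says how, and this plan gives neither an imputation method nor a missing-scan rule. Someone without usable MRI therefore leaves the tests of attention, working memory and executive function as well, although none of those scores, nor the learning outcomes, needs a scan.

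Two things are at stake. One is precision for three of the five Aim 2 predictions. The other, which matters more, is who is left in. Because the study scan is conditional on learning, the people most likely to be absent are those who learn on no task, at the low end of the outcome that the models try to explain. The protocol justifies the learning requirement by the intended use of the brain-scan data. That reasoning does not extend to an analysis of cognition and learning, which needs no scan.

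**Working it through.** **Plan's own figures.** Fixed-model F test with noncentrality λ = f²·N and df = (p, N−p−1), alpha .05.
- Two predictors, f² = .25, N = 50: power .875, against a stated value above .90 (N = 54 would be needed).
- Three predictors, f² = .28, N = 49: power .858, which agrees with the stated 85%.

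The first discrepancy is a separate matter, and nothing below depends on it.

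**Who is missing.** Specific Aims, Aim 1 reports "equal percentages of learners of type a, c and d (20% of pilot participants in each stratification", type d being people who learn under no condition. Taking type d as those who fail the scan's learning requirement, 75 × .20 = 15 would not be offered the study scan and 75 × .80 = 60 would pass. The protocol gives no rate for MRI ineligibility. If 10%, 20% or 30% of the 60 lack usable MRI (assumption), 54, 48 or 42 remain. Clinical scans would add some people back; attrition would remove some.

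**Attention.** Inputs from the power section: r = .38 (striatum) and r = .32 (attention). Predictors are assumed uncorrelated.
- R² of the planned model = .38² + .32² = .1444 + .1024 = .2468.
- f² for the attention coefficient in that model = .1024 / (1 − .2468) = .136.
- f² for attention alone = .1024 / (1 − .1024) = .114.

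| Model | N | Power |
|---|---|---|
| Planned, attention coefficient (1 df) | 42 | .64 |
| Planned | 48 | .71 |
| Planned | 50 | .72 |
| Planned | 54 | .76 |
| Planned | 60 | .80 |
| Planned | 65 | .83 |
| Attention alone | 70 | .80 |
| Attention alone | 75 | .82 |

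**Working memory plus executive function.** The protocol gives r = .34 for prefrontal cortex, and a range of .25 to .72 for executive functions, attention and learning. It gives no working-memory correlation. I assume r = .25 for each of the two, with all predictors uncorrelated.
- R² of the planned model = .34² + .25² + .25² = .1156 + .125 = .2406.
- f² for the cognitive pair in that model = .125 / (1 − .2406) = .165.
- f² for the pair alone = .125 / (1 − .125) = .143.

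| Model | N | Power (2 df) |
|---|---|---|
| Planned, cognitive pair | 49 | .69 |
| Planned | 60 | .79 |
| Pair alone | 75 | .83 |

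As a range check, the cognitive share can be taken from the plan's own f² = .28 instead: R² = .28/1.28 = .219, less .34² = .116, leaves .103. Power is then .59 at N=49 and .69 at N=60 in the planned model, against .73 for the pair alone at N=75. The levels are lower, but the pattern is the same.

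These calculations hold the correlations fixed. They do not include any effect of the learning requirement on the range of the outcome.

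**The case against.** The strongest reply is that the planned model is not weak for these tests. The lesion term removes residual variance, so with 60 usable scans the attention coefficient is within about 2 points of what attention alone would give at N=75, and with 65 it has slightly more power. This stands, and it is why the precision argument is modest.

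A reader might infer something stronger: that a third of the data is discarded, with attention power falling from .82 at N=75 to .65 at N=50. The documents do not support that. The .65 is for attention alone at N=50, a model that the protocol does not fit. The 50 and 49 are power targets, not scan counts. The 75 is a ceiling that includes an allowance for attrition.

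A reader might also infer that all non-learners are excluded. They are not: a clinical MRI can stand in for the study scan, and a person who fails one task but learns on another still qualifies. Claustrophobia is likewise only a screening consideration, and those affected may continue if they wish.

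It is fair to add that restriction to complete cases is inferred from the absence of a rule, that the section is headed a brief overview, and that its wording on what enters the models first may hint at later ones. But no later model is stated. Finally, a cognition-only coefficient may be confounded by lesion extent, so such models should not displace or precede the stated ones.

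**Conclusion.** The point holds in a limited form. As written, the attention, working-memory and executive-function predictions are tested only in people with usable study or clinical MRI, and that sample is partly selected on learning. About 15 of 75 would be ineligible for the study scan at the pilot share (from eighteen people, so imprecise), and most of these would be missing unless they have a clinical MRI.

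The power gain from using everyone depends on the unstated scan count. For attention it is about 10 points if 50 have usable MRI (.72 to .82) and 2 points if 60 do (.80 to .82). For the cognitive pair it is about 14 points from N=49 (.69 to .83) and 4 from N=60 (.79 to .83). These gains assume uncorrelated predictors, r = .25 for each member of the pair, and all 75 with complete behavioural data; at 70, attention alone has .80. The main benefit is therefore less selection on the outcome, with some precision gained if only about 50 have usable MRI.

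**What to change.** Keep the stated lesion-plus-cognition models for the regional predictions and for whether cognition adds to lesion. Beside them, pre-specify supplementary cognition-only models in everyone who has the relevant learning score and composites:
- attention for SRT;
- attention for AGL;
- working memory and executive function for rule-based learning.

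Report the sample size of each model. State that the cognition-only coefficients are not adjusted for lesion and should be read next to the MRI-sample results. State also how people without spared-tissue data are handled in the main models.

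The cost is three extra regressions on data already planned, with no new visits or measures. They add three tests, so they should be labelled supplementary and fixed before analysis.

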assigned a binary value (1 or 0), are normalized from native to MNI space (a standard brain space utilized in imaging studies). The individualized lesion map is subtracted from each brain region of interest (ROI) to yield the volume of spared tissue per ROI. The percentage of spared tissue in each region is calculated by dividing the volume of spared tissue by the total volume of the MNI atlas ROI. We will use MATLAB to identify the union of lesion maps and anatomical ROIs from the MNI template to compute lesion volume and percent spared tissue for each ROI. Percent spared tissue in ROIs will be entered into regression models evaluating predictors of learning.

Cognitive Linguistic Assessments: Language and cognitive assessments will be scored based on norms and methods of administration and scoring provided in testing manuals and publications.

Composite scores of sustained attention, executive function, and auditory-verbal working memory will be computed for entry into regression models.

Data Analyses: Linear regression models will be run to determine the predictors of learning. Separate models will be examined for SRT observational, AGL observational and rule-based and learning. The dependent variable for SRT observational learning will be Cohen's d effect size for the first round of learning computed in Aim 1. The dependent variable for AGL observational learning will be percent correct in testing computed in Aim 1. The dependent variable for AGL observational learning will be percent accuracy obtained in Aim 1. We anticipate that accuracy rates will fall between .2 and .8 which is recommended if accuracy rates are to be used as a dependent variable for a linear regression. If scores fall outside of this range, we will switch to a logistic regression model where number of successes and the total number of trials are incorporated into the analysis.

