Describe the plan for monitoring the data to ensure the safety of subjects. The plan should include a brief description of (1) the safety and/or efficacy data that will be reviewed; (2) the planned frequency of review; and (3) who will be responsible for this review and for determining whether the research should be altered or stopped. Include a brief description of any stopping rules for the study, when appropriate. Depending upon the risk, size and complexity of the study, the investigator, an expert group, an independent Data and Safety Monitoring Board (DSMB) or others might be assigned primary responsibility for this monitoring activity.

NOTE: Regardless of data and safety monitoring plans by the sponsor or others, the principal investigator is ultimately responsible for protecting the rights, safety, and welfare of subjects under his/her care.

Forms containing personally identifying information such as contact information and questions related to eligibility, are programmed in RedCap with responses directly entered into RedCap. Cognitive-linguistic assessment data is collected on paper forms that will be kept in a locked filing cabinet at the MGH-IHP to which only the PI and approved study staff have access. Information will be transferred into a secure HIPAA compliant web-based application: RedCap to which only approved researchers have access.

Digital data (such as study reaction time, accuracy files, certain cognitive-linguistic assessments such as the TALSA and eye tracking data) will initially be collected on an encrypted, password protected laptop (accessed by the PI and study staff) or desktop computer. Data will be transferred to Dropbox, a secure network or web-based electronic lab notebook, LabArchives, maintained by MGB, which can only be accessed by the PI and approved study staff via electronic ID. These digital files will be coded with identification codes and will not contain personally identifiable information. Deidentified standardized assessment scores will be transferred from paper forms to digital forms in RedCap. Video data will be recorded and kept on MGB Dropbox and accessed only by approved researchers. Deidentified video clips will be kept for education purposes.

MRI imaging data obtained at the Martinos Center are stored and analyzed on an MGB-hosted secure cluster to which only approved research staff have access.

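### The Aim 2 regressions leave out age in an 18-to-80 sample and do not say whether the cognitive composites are age-adjusted, so a cognitive predictor of learning could partly reflect age

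*Combined protocol and SAP*

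**What the plan says.** Under Aim 2, Data Analyses, in the overview of statistical methods, the observational learning analysis is "a regression model with two predictors: percent spared tissue in the striatum and cognitive scores of attention". The rule-based analysis is "a regression model with three predictors: percent spared tissue in the prefrontal cortex and cognitive scores of working memory and executive function". For each, the plan evaluates the significance of the model and the variability accounted for. The text presents these as the models to be run first, but specifies no later ones.

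Age appears only as an eligibility criterion: "Be between the ages of 18 and 80 years of age". It is not in the list of data to be collected or among the variables that Aim 2 names. The Data and Safety Monitoring section says that "questions related to eligibility, are programmed in RedCap with responses directly entered into RedCap", so age should be on file, but that is an inference.

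On the cognitive scores, the plan says: "Language and cognitive assessments will be scored based on norms and methods of administration and scoring provided in testing manuals and publications". Composites are then built for the regressions. The plan does not say whether those norms adjust for age or whether the composites use adjusted scores.

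On the outcomes: "The dependent variable for SRT observational learning will be Cohen's d effect size for the first round of learning computed in Aim 1". The two grammar tasks use accuracy at test. No age standardisation is stated for any outcome.

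**The concern.** Age could plausibly relate both to cognitive test performance and to performance on the learning tasks, and a 62-year eligibility window (80 − 18) leaves room for it to do so. The protocol itself notes that the eye-tracking task was piloted separately in young and older adult controls. If age moves attention and learning in the same direction, a regression without age credits attention with what belongs to age.

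Spared tissue cannot stand in for age. It is lesion overlap expressed against a fixed atlas volume, so as defined it measures the lesion and not age-related volume change.

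Aim 2 compares the predictors found with theoretical accounts of learning, and the longer-term purpose is to tailor therapy to the patient. An association produced by age would be read as support for the predicted cognitive contribution. The pilot correlation of .32 between attention and implicit learning, used in the sample-size section, is not stated to be age-adjusted either.

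**Working it through.** **Inputs from the documents.** Observational model: two predictors, f² = .25, N = 50, planning correlations .38 (striatum) and .32 (attention). Rule-based model: three predictors, f² = .28, N = 49. Power was "conducted in G*Power to determine a sufficient sample size using an alpha of 0.05". Planned enrolment is 75; the number with usable scans is not stated.

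**Input not in the documents.** The correlation of age with attention and with learning. I set both to the same value r, in the same direction, and vary r from .1 to .5.

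**1. The plan's own power figures.** The test is a noncentral F with λ = f²·N and df = (predictors tested, N − all predictors − 1).
- Rule-based: λ = .28 × 49 = 13.72, df (3, 45), power .8584. The stated N = 49 for 85% power reproduces.
- Observational: λ = .25 × 50 = 12.5, df (2, 47), power .8752. The plan states more than .90, which on this test needs N = 54. That gap is a separate matter and does not affect this point.

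**2. What omitting age can do.** If attention has no direct effect, age alone induces an attention–learning correlation of r × r: .09 at r = .3 and .25 at r = .5. These are 28% and 78% of the pilot .32. The table gives simulated rejection rates at N = 50 and alpha .05, with attention and striatum both having no direct effect.

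| r (assumed) | Whole-model test, no age | Attention coefficient, no age | Attention coefficient, age in model |
|---|---|---|---|
| .1 to .2 | 5–6% | 5–6% | about 5% |
| .3 | about 8% | about 10% | about 5% |
| .4 | about 16% | about 20% | about 5% |
| .5 | about 34% | about 43% | about 5% |

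Repeat runs agree to about one percentage point. The joint test of both predictors given age also rejects in about 5%. If attention is unrelated to age, as full age-norming would aim for, the coefficient rejects in about 5% with or without age in the model.

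**3. Cost if the age-adjusted effect size is unchanged.** The hypothesised predictors are tested jointly with age in the model, so only the denominator df changes.
- Observational, df (2, 46): power .8752 becomes .8747.
- Rule-based, df (3, 44): power .8584 becomes .8576.

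**4. Cost if age is a real confounder.** f² = .25 means R² = .25/1.25 = .20. The planning correlations give .38² + .32² = .2468 if uncorrelated, so scale both by √(.20/.2468) = .900. That gives .342 for striatum (squared, .117) and .288 for attention (squared, .083). Take striatum as independent of age and attention. Then:
- R²(attention, age) = (.083 + r² − 2 × .288 × r²)/(1 − r²)
- R²(full) = .117 + R²(attention, age)
- partial f² = (R²(full) − r²)/(1 − R²(full))

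At r = .3, R²(full) = .117 + .133 = .250, and partial f² = .160/.750, about .214. At r = .4 and .5 it is .194 and .188. Joint power at N = 50 is then .815, .775 and .762.

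**The case against.** The best case for the plan has four parts.

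*Norm-based scoring may already remove age from the cognitive scores.* If it does so fully, there is no inflation. This stands as a possibility, but the text does not say it, which is why the fix asks for a statement.

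*The SRT outcome is a within-person effect size.* Slowing that stretches every reaction time proportionally scales the difference and the pooled standard deviation alike, and so cancels. This also stands. It does not cover age differences in the learning itself, and it offers nothing for the two accuracy outcomes.

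*Aim 2 never names age, and choosing covariates is a matter of judgement.* This is fair. A reader might infer that the plan contradicts itself by omitting age. It does not: age is not among the Aim 2 variables, and the point is an improvement to the analysis.

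*The harm rests on outside values.* This is true. A reader might go further and infer that any cognitive effect found will be an age effect. The documents give no age correlation and cannot support that; at correlations of .1 to .2 the rejection rates are close to nominal.

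A reader might equally infer that adjustment is free. That holds only if the adjusted f² stays at its planned value. Where the confounding is real, adjustment costs about 6 to 11 points of power against the planned effect.

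One further worry does not count against adjusting. If age affects learning through attention, age is upstream, and including it costs precision without biasing the attention coefficient.

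**Conclusion.** The concern holds in a conditional form. The models omit age across an 18-to-80 range, no age-adjusted analysis is described, and the norming of the composites is left open. A cognitive association with learning can therefore partly reflect age. The possible size runs from nothing (composites fully age-normed, or age correlations of .1 to .2) to whole-model rejection in about 34% of studies and attention-coefficient rejection in about 43% (age correlations of .5). These figures assume same-direction age effects, no direct effect of attention or striatum, and N = 50. They describe what the plan leaves open and do not estimate what will happen in this sample. That age is on file is inferred from the eligibility criterion and the electronic eligibility form.

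**What to change.** Before analysis, prespecify age as a continuous covariate in the SRT, AGL and rule-based models, and in the logistic models if the accuracy fallback is used. Test the hypothesised predictors jointly given age, and report the unadjusted model alongside. State whether the composites use age-adjusted scores, and confirm that age is held as an analysis variable.

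The test must be the joint one. Counting age within the whole-model F at the same f² gives power of .822 (N = 50) and .814 (N = 49), and a significant result could then be due to age alone.

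No new data collection should be needed. The cost is one degree of freedom if the age-adjusted f² is unchanged; N for .90 power in the observational model stays at 54, and N for .85 in the rule-based model stays at 49. If age is a real confounder at .3 to .5, expect power of about .82 to .76 in the two-predictor model at N = 50. That loss is the part of the planned effect that belonged to age, and the sample-size section should acknowledge it.
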